4.1.3. Cardiac Imaging

Healing post LAAO includes endothelialization of the LAA device. In a preclinical canine model, the PET fabric membranes of implanted WATCHMAN devices showed an organized neoendocardial surface at 45 days with endothelialization well under way by 90 days²⁸. Human necropsy hearts showed similar healing stages, though animal healing was faster²⁸.

In patients, pre-procedural anatomical assessment of the LAA with TEE, CT, or cardiac magnetic resonance imaging (MRI) is used to determine the technical feasibility and safety of LAA occlusion, including device sizing and optimal implant positioning. A multimodality integrated approach including angiography, TEE, and/or intracardiac echocardiography (ICE) provides intraprocedural guidance and confirmation of LAA closure²⁹⁻³¹. After the procedure, imaging surveillance at follow-up allows assessment of device tissue coverage, peri-device leaks, and device-related thrombus (DRT), which has been observed with various LAAO devices and may be associated with late thromboembolic events³²⁻³⁷.

The current WATCHMAN FLX Instructions for Use (IFU) recommends use of TEE at 45 days post device implant to check for the presence of intra-cardiac thrombus as well as to detect and measure any residual flow around the device. The objective of the WATCHMAN FLX CT study is to assess device endothelialization at several time points in addition to the recommended 45 days using serial CT and TEE and assess its relationship, if any, to clinical events.

4.2. *Study Rationale*

The purpose of the WATCHMAN FLX CT study is to evaluate the device tissue coverage post-implantation using serial advanced imaging modalities such as CT and TEE and assess its relationship, if any, to clinical events.

5. Commercial Device Description (part of Standard of Care)

As per the product Instructions for Use (IFU), the WATCHMAN FLX™ Left Atrial Appendage Closure Device (Boston Scientific Corporation, Marlborough, MA, USA) is intended to prevent thrombus embolization from the left atrial appendage (LAA) and reduce the risk of life-threatening bleeding events in patients with non-valvular atrial fibrillation who are eligible for anticoagulation therapy or who have a contraindication to anticoagulation therapy. Please see the product IFU for any contraindications.

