Endpoints are listed below. Measurements will be collected peri- and post-procedure, predischarge, and at 14 days, 45 days, 3 months and 12 months after the implant procedure, unless specified otherwise.

The primary endpoint is device surface morphology (inclusive of tissue coverage) post implant procedure as assessed over time using the serial advanced imaging modalities of cardiac computed tomography (CT) and transesophageal echocardiography (TEE).

Additional endpoints will include the following:

- Endpoints adjudicated by an Independent Clinical Events Committee (CEC):
 - All-cause mortality (cardiovascular/unknown and non-cardiovascular)
 - Stroke (disabling and non-disabling; ischemic and hemorrhagic)
 - **Note 1:** For subjects diagnosed with a neurological event (e.g., stroke, transient ischemic attack [TIA]), mRS and NIHSS should be performed after the event. It is recommended that the subject be contacted regarding mRS assessment at 90 ± 14 days following any suspected stroke; the simplified mRS questionnaire³⁸ may be used for this follow-up assessment. It is recommended that imaging be performed after the event to screen for device related thrombus (DRT). If performed, imaging results should be sent to the core laboratory.
 - Systemic embolism
 - Bleeding: International Society on Thrombosis and Haemostasis (ISTH) major and non-major clinically significant
 - Procedural bleeding (≤ 7 days post-procedure)
 - Non-procedural bleeding (> 7 days post-procedure)
 - Pericardial effusion/tamponade requiring pericardiocentesis or surgery
- Endpoints not adjudicated by an Independent Clinical Events Committee (CEC):
 - Device success: defined as implantation of a WATCHMAN FLX device without in-hospital mortality
 - Assessments by serial imaging modalities (CT and TEE, optional cardiac magnetic resonance imaging [MRI]) at 14 days, 45 days, and 3 months (TEE optional at 3 months if there is no leak at 45 days). Data will be evaluated by an independent core lab.
 - Device seal at 45 days post index implant procedure (see **Note 2**)
 - Device-related thrombus (including hypoattenuated thickening [HAT] per CT analysis)
 - Device surface morphology (inclusive of tissue coverage) post implant procedure as assessed over time

Note 2: Results are classified as no leak, leak > 0 and ≤ 5 mm, or leak > 5 mm

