Abbreviations: eCRF=electronic case report form; ICF=Informed Consent Form; LAA=left atrial appendage

10. Study Methods

10.1. *Data Collection*

This section lists the data needed to fulfill the objectives of this clinical study.

The data collection schedule is provided in **Table 10.1-1** and summarized diagrammatically in **Figure 10.1-1**. Additional information, including recommended post-procedure medical therapy, is provided in Section **10.2** through Section **10.10**.

Table 10.1-1: WATCHMAN FLX CT Study Event Schedule

Assessment	Baseline	Index Procedure	Predischarge	14 Days ^a (\pm 3 Days)	45 Days ^a (\pm 15 Days)	3 Months ^a (90 ± 30 Days)	12 Months ^a (365 ± 30 Days)
Signed Informed Consent Form (date)	X	—	—	—	—	—	—
Demographics	X	—	—	—	—	—	—
Medical history and inclusion/exclusion criteria	X	—	—	—	—	—	—
Physical assessment	X	—	—	—	X	X	O
Risk factor assessments ^b	X	—	—	—	—	—	—
TEE of LAA ^c	X ^c	—	—	X	X	X ^c	O ^d
CT of LAA ^c	X ^c	—	—	X	X	X	O
MRI of LAA ^e	O	—	—	O	O	O	O
Labs – biochemical markers ^f	X	—	—	X	X	X	O
NIHSS Stroke Scale ^g	X	—	—	—	—	—	—
Modified Rankin Scale score ^g	X	—	—	—	—	—	—
Procedural ICE ^h	—	X	—	—	—	—	—
Medications	X	X	X	X	X	X	X
SAE, ADE, SADE, USADE, procedure-related AE and device deficiencies ⁱ	—	X	X	X	X	X	X

Note 1: X = should be performed; O=optional (unless required based on other data); — = not required

Baseline assessments should be done within 30 days unless specified otherwise in the footnotes below. Eligibility for the study is determined per standard of care. Any additional study specific testing to verify inclusion/exclusion criteria must be done after the ICF is signed.

a: All follow-up dates will be calculated from the date of the (attempted) index procedure. Subjects are considered enrolled in the study when the subject or the subject's legally authorized representative signs an ICF approved by the Independent Ethics Committee. Clinical follow-up is in-person at 14 days, 45 days, and 3 months. Follow-up at 12 months is in-person (preferred) or by telephone (unless an in-person assessment is required based on other data). Subjects who are enrolled but do not have a WATCHMAN FLX™ LAA Closure Device implanted in the correct position will be followed for safety through 12 months after the initial attempted index procedure but will not undergo imaging assessments or evaluation of biochemical markers.

b: Risk factor assessments include HAS-BLED and CHA₂DS₂-VASc scores.

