c: Either TEE or CT must be done within 14 days prior to the index procedure (baseline assessment) following the core laboratory guidelines (see Section 12.3). CT at 14 days, 45 days, and 3 months are required for all subjects who have a WATCHMAN FLX™ LAA Closure Device implanted in the correct position and should be performed per the core lab guidelines. TEE is required at 14 days, 45 days and optional at 3 months if there is no leak at 45 days, for all subjects who have a WATCHMAN FLX™ LAA Closure Device implanted in the correct position and should be performed per the core lab guidelines. Results must be sent to the core laboratory for independent analysis (see Section 12.3).

Table 10.1-1: WATCHMAN FLX CT Study Event Schedule

Assessment	Baseline	Index Procedure	Predischarge	14 Days ^a (\pm 3 Days)	45 Days ^a (\pm 15 Days)	3 Months ^a (90 ± 30 Days)	12 Months ^a (365 ± 30 Days)
------------	----------	-----------------	--------------	---	--	--	--

- d: Repeat TEE should be done at 12 months if the 3-month TEE assessment suggests a leak > 5mm or the 3-month CT assessment suggests a leak > 3mm; results must be sent to the core laboratory.
- e: MRI imaging assessments are optional. If MRI assessment is done, core laboratory guidelines should be followed. Results must be sent to the core laboratory for independent analysis (see Section 12.3).
- f: Labs include biochemical markers including measures of coagulation, platelet and endothelial activation and inflammation. At baseline, these labs should be obtained within 30 days prior to the index procedure. Baseline serum creatinine is also required but may be obtained up to 180 days prior to consent.
- g: Baseline neurological assessments should be done within 30 prior to the index procedure. For subjects diagnosed with a neurological event (e.g., stroke, TIA), mRS and NIHSS should be performed after the event. It is recommended that the subject be contacted regarding an mRS assessment at 90 ± 14 days following any suspected stroke; the simplified mRS questionnaire may be used for this follow-up assessment and may be collected by telephone.
- Note 2:** If a subject has a stroke or other thromboembolic event, work-up should occur as per local standard of care. It is recommended that imaging be performed to screen for DRT. If performed, imaging results should be sent to the Core Laboratory.
- h: Procedural ICE data should be sent to the Core Laboratory.

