All subjects successfully implanted with a WATCHMAN FLX device will be evaluated at 14 days, 45 days, 3 months, and 12 months post index procedure. Subjects who are enrolled but not implanted with a WATCHMAN FLX device in the correct position will be followed for safety through 12 months after the initial attempted index procedure but will not undergo imaging assessments or evaluation of biochemical markers including measures of coagulation, platelet and endothelial activation and inflammation.

It is important that this schedule be maintained as closely as possible for all subjects. Boston Scientific Corporation (BSC) recognizes that subjects may not be able to return for all scheduled visits at precisely the date required, and therefore, a period of time in which each visit is allowed is indicated in **Table 10.1-1**. Required follow-up assessments and visits not completed will be considered missed visits and recorded as protocol deviations. Visits completed outside follow-up windows will be recorded as protocol deviations. Each follow-up visit must be performed by trained study personnel. Data from collected tests and images

as well as medical assessments will be recorded in source documentation and captured in the eCRFs.

In the event that study personnel learn of a subject's hospitalization outside the study center, the center should make every effort to obtain copies of reports or results based on tests (e.g., echocardiogram) and/or procedures performed on the study subject.

10.8.1. 14-Day Follow-up (14 Days \pm 3 Days)

All enrolled subjects will be evaluated 14 days after the index procedure. The study eCRFs identify the specific data points to be collected as listed below.

- Complete safety event assessment, including any SAE, ADE, SADE, USADE, device deficiency with associated treatment, and any CEC event regardless of seriousness and device relationship.

Note 1: For subjects diagnosed with a neurological event (e.g., stroke, TIA), mRS and NIHSS should be performed after the event. It is recommended that the subject be contacted regarding an mRS assessment at 90 ± 14 days following any suspected stroke; the simplified mRS questionnaire may be used for this follow-up assessment and may be collected by telephone. It is also recommended that imaging be performed to screen for DRT. If performed, imaging results should be sent to the core laboratory.

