- All antiplatelet medications, which should be administered in accordance with local standard of care. Subjects must be treated with SAPT (aspirin or P2Y₁₂ inhibitor) for at least 3 months following WATCHMAN FLX implantation.
- Assessment of biochemical markers including measures of coagulation, platelet and endothelial activation and inflammation.
- TEE is required for all subjects who have a WATCHMAN FLX™ LAA Closure Device implanted in the correct position and should be performed per the core lab guidelines, including assessment of device seal and device surface morphology (inclusive of tissue coverage) post implant procedure. Results must be sent to the core lab for independent analysis.
- CT is required for all subjects who have a WATCHMAN FLX™ LAA Closure Device implanted in the correct position and should be performed per the core lab guidelines, including assessment of device seal, device-related thrombus (including hypoattenuated thickening [HAT]) and device surface morphology (inclusive of tissue coverage) post implant procedure. Results must be sent to the core lab for independent analysis.
- Cardiac MRI assessment, including 4D cardiac MRI flow analysis of the LA and LAA, is optional but if performed, the results must be sent to the core lab for independent analysis.

Subjects who are enrolled but not implanted with a WATCHMAN FLX device in the correct position during the index procedure will be followed for safety through 12 months after the initial attempted index procedure but will not undergo imaging assessments or evaluation of

biochemical markers including measures of coagulation, platelet and endothelial activation and inflammation.

10.8.2. 45-Day Follow-up (45±15 Days) and 3-Month Follow-up (90±30 Days)

All enrolled subjects will be evaluated 45 days and 3 months after the index procedure. The study eCRFs identify the specific data points to be collected as listed below.

- Complete safety event assessment, including any SAE, ADE, SADE, USADE, device deficiency with associated treatment, and any CEC event regardless of seriousness and device relationship.

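### Does the 3-month visit window open too early to keep the 3-month scan distinct from the 45-day scan?

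*Protocol*

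**What the plan says.** Section 10.8.2 gives the two windows in its heading: "45-Day Follow-up (45±15 Days) and 3-Month Follow-up (90±30 Days"). The header of Table 10.1-1 agrees, and footnote a fixes day zero: "All follow-up dates will be calculated from the date of the (attempted) index procedure". The other follow-up visits are at 14±3 and 365±30 days.

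Section 10.8 asks that the schedule be followed as nearly as possible and presents the windows as an allowance for subjects who cannot attend on the exact date. It adds: "Visits completed outside follow-up windows will be recorded as protocol deviations". No minimum interval between two visits is stated.

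In Section 6.2, "The primary endpoint is device surface morphology (inclusive of tissue coverage) post implant procedure as assessed over time", using serial CT and TEE. CT is required at 14 days, 45 days and 3 months. For TEE, footnote c of Table 10.1-1 says "TEE is required at 14 days, 45 days and optional at 3 months if there is no leak at 45 days". The synopsis states that there is no formal hypothesis and that no inference will be made.

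**The concern.** Two compliant CTs that are meant to be 45 days apart could fall on the same day or a few days apart, and neither would be recorded as a deviation. The 3-month window is also the only one containing days nearer to another visit's target than to its own.

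The background in Section 4.1.3 seems to make this important. It describes an "organized neoendocardial surface at 45 days with endothelialization well under way by 90 days", so a reading at day 60 labelled as 3 months might show the earlier stage. With at most 25 subjects, three scheduled imaging visits, and TEE optional at 3 months in subjects without a leak at 45 days, the last step of the time course may rest on CT alone. The same CT enters the condition for a 12-month TEE, which depends in part on whether "the 3-month CT assessment suggests a leak > 3mm". A blurred 3-month time point would weaken the description of the primary endpoint.

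**Working it through.** **Inputs.** Targets and half-widths come from Table 10.1-1 and Sections 10.8.1 to 10.8.3: 14±3, 45±15, 90±30 and 365±30 days from the index procedure.

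**Windows (target ± half-width).** Days 11–17, 30–60, 60–120 and 335–395. The only overlap is day 60.

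**Distance to targets.** The midpoint of 45 and 90 is (45 + 90)/2 = 67.5.

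| Day | Distance to 45 | Distance to 90 |
|---|---|---|
| 60 | 15 | 30 |
| 67 | 22 | 23 |
| 68 | 23 | 22 |

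Days 60–67 are therefore nearer to 45: 8 of the 120 − 60 + 1 = 61 days in the window. No other window contains such a day, although day 30 passes narrowly (15 days from 45, 16 from 14). The cause is the position of the midpoint, not the shared day. The count also depends on the scale: on a ratio scale the midpoint is √(45 × 90) = 63.6, and only days 60–63 (4 of 61) are affected.

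**Gap between the two scans.** Smallest 60 − 60 = 0, largest 120 − 30 = 90, nominal 45. For the preceding pair the smallest gap is 30 − 17 = 13 days.

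**How often this could happen.** The protocol gives no distribution of scan days, so three are assumed, with the two visits independent:

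- uniform over each window;
- triangular, peaking on the target (weight 31 − |day − 90| for the 3-month visit, total 31² = 961; the 45-day visit likewise);
- clustered: normal with SD 5 days (45-day visit) and 10 days (3-month visit), cut at the window limits.

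Uniform, days 60–67: 8/61 = 13.1%. Triangular: (1 + 2 + … + 8)/961 = 36/961 = 3.7%. For gaps under 13 days, a gap of g days arises from g + 1 day pairs, so the count is 1 + 2 + … + 13 = 91 of 31 × 61 = 1,891 pairs, or 4.8% under the uniform assumption.

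| | Uniform | Triangular | Clustered |
|---|---|---|---|
| 3-month scan on days 60–67 | 13.1% | 3.7% | 1.1% |
| of 25 subjects | 3.3 | 0.9 | 0.3 |
| Gap under 13 days | 4.8% | 0.74% | 0.11% |
| of 25 subjects | 1.2 | 0.19 | 0.03 |

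A same-day pair has probability 1/1,891 = 0.05% even in the uniform case. Independence tends to overstate the close pairs: if subjects who come late once tend to come late again (an assumed correlation of 0.5, normal copula), the share under 13 days falls to about 1.0% (uniform) and 0.03% (triangular), and to almost nothing when clustered.

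**What a narrower window would do.** Opening on day 75 excludes days 60–74: 15/61 = 24.6%, 120/961 = 12.5% and 5.95%, that is 6.1, 3.1 and 1.5 of 25 visits. Under each assumption this exceeds the number on days 60–67 (3.3, 0.9, 0.3). The SD of the interval would fall from 19.7 to 16.0, from 14.2 to 12.4, and from 11.05 to 10.1 days. The largest gap stays at 90 days.

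**The case for a change.** The best argument for the concern is that visit windows are fixed in the protocol and cannot be repaired later. An analysis plan can relabel a scan or use its actual day, but it cannot supply a later observation that was never made. With so few imaging visits, a near-duplicate pair loses information on the primary endpoint, and the general request to keep to schedule sets no enforceable limit. Narrowing the window would need no extra visit or scan.

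Part of this stands: the early limit is loose, and the protocol shown has no rule for a scan on day 60. The rest does not make it a fault:

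- The nearer-target test is brought in from outside. The protocol neither states it nor relies on it, and its result changes with the scale.
- The healing stages are from dogs. The same paragraph says "Human necropsy hearts showed similar healing stages, though animal healing was faster", so it gives no human stage for day 45, 60 or 90. Calendar distance cannot be read as biological stage, and nothing shows that a scan on days 60–67 would change a leak reading.
- The larger figures need scan days spread evenly over the window, which sits badly with the instruction in Section 10.8.
- A narrower window has costs: fewer compliant days, probably more recorded deviations, and ethics committee approval of the amendment (Section 14.3). The revision history shows that the sponsor has already lengthened the baseline imaging period from 7 to 14 days for scheduling reasons.

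**Conclusion.** The concern does not hold. The window arithmetic is right, but it reveals no contradiction and no stated rule that gives a wrong result. Two adjacent windows that meet on one day are workable. That day can be resolved by ordinary visit assignment or by analysing the actual scan day, which a protocol may leave to the analysis plan. No test, error rate or statistical decision rule is affected.

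The size is small if sites aim for the target dates: about 0.3 (clustered) to 0.9 (triangular) of 25 subjects on days 60–67, and 0.03 to 0.19 with scans under 13 days apart. The uniform assumption gives 3.3 and 1.2 and is best read as a pessimistic case. All these figures rest on assumed scan-day distributions, and the close-pair figures also on independent visit dates. A later opening day buys modestly tighter spacing at the price of scheduling freedom, so it is a design preference and not a correction.

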11.2.2. Control of Systematic Error/Bias

The selection of subjects will be made from the Investigator's usual case load. The study center's heart team assessments and imaging measurements before device placement will contribute to the determination of subject eligibility for the study. All subjects who have signed the ICF and are selected to receive a study device will be enrolled in the study (see Section 9.1 for point of enrollment).

To control for inter-observer variability, data from an independent core laboratory (see Section 12) will be used for analysis at pre-specified time points. An independent CEC (see Section 19.1.1) will adjudicate study endpoint related clinical events (see Section 6.2).

11.2.3. Number of Subjects per Investigative Center

A single center may enroll up to 25 subjects.

11.3. Data Analyses

Baseline and outcome variables will be summarized using descriptive statistics for continuous variables (mean, standard deviation, number of observations, minimum and maximum) and discrete variables (percentage and count/sample). Study endpoints are listed in Section 6.2.

Any changes to the planned statistical analyses made prior to performing the analyses will be documented in an amended statistical analysis plan approved before performing the analyses. Changes from the planned statistical methods after performing the analyses will be documented in the clinical study report along with a reason for the deviation.

12. Data Management

12.1. Data Collection, Processing, and Review

Subject data will be recorded in a limited access secure electronic data capture (EDC) system.

The clinical database will reside on a production server hosted by Medidata EDC System. All changes made to the clinical data will be captured in an electronic audit trail and available for review by BSC or its representative. The associated Rave software and database have been designed to meet regulatory compliance for deployment as part of a validated system compliant with laws and regulations applicable to the conduct of clinical studies pertaining to the use of electronic records and signatures. Database backups are performed regularly.

The Investigator provides his/her electronic signature on the appropriate electronic case report forms (eCRFs) in compliance with local regulations. A written signature on printouts of the eCRFs must also be provided if required by local regulation. Changes to data previously submitted to BSC require a new electronic signature by the Investigator acknowledging and approving the changes.

Visual and/or electronic data review will be performed to identify possible data discrepancies. Manual and/or automatic queries will be created in the Medidata EDC system and will be issued to the center for appropriate response. Center staff will be responsible for resolving all queries in the database.

All access to the clinical database will be changed to “Read Only” after all data are either “Hard Locked” or “Entry Locked.” Once acceptance of the final study report or finalization of publications (as applicable) is received, final database storage and archiving activities can begin. When all closeout activities are completed, a request to the BSC Information Technology department is submitted to have the database locked or decommissioned and all database access revoked.

12.2. *Data Retention*

The Principal Investigator or his/her designee or investigational center will maintain all essential study documents and source documentation that support the data collected on the study subjects in compliance with applicable regulatory requirements.

The Principal Investigator or his/her designee will take measures to prevent accidental or premature destruction of these documents. If for any reason the Principal Investigator or his/her designee withdraws responsibility for maintaining these essential documents, custody must be transferred to an individual who will assume responsibility and BSC must receive written notification of this custodial change. Centers are required to inform BSC in writing where paper or electronic files are maintained in case files are stored off site and are not readily available.

12.3. *Core Laboratory*

Echocardiography images, CT data, and MRI data (if applicable) will be evaluated by an independent core laboratory. Procedure guidelines for the required imaging assessments are provided by the core laboratory in the Manual of Operations. These analyses will minimize bias and inconsistencies by providing an independent interpretation of all measurements using standard techniques.

13. Deviations

An Investigator must not make any changes or deviate from this protocol, except to protect the life and physical well-being of a subject in an emergency. An investigator shall notify BSC and the reviewing IEC of any deviation from the investigational plan to protect the life or physical well-being of a subject in an emergency, and those deviations which affect the scientific integrity of the clinical investigation. Such notice shall be given as soon as possible, but no later than 5 working days after the emergency occurred, or per prevailing local requirements, if sooner than 5 working days.

All deviations from the investigational plan, with the reason for the deviation and the date of occurrence, must be documented and reported to BSC using the EDC CRF. Centers may also

be required to report deviations to the IEC and the regulatory authority, per local guidelines and government regulations.

Deviations will be reviewed and evaluated on an ongoing basis and, as necessary, appropriate corrective and preventive actions (including IEC/Regulatory Authority notification, center re-training, or center discontinuation/termination) will be put into place by BSC.

The sponsor will not approve protocol waivers.

14. Compliance

14.1. *Statement of Compliance*

This clinical investigation is financed by the study sponsor. Before an investigational center can be considered “Authorized to Enroll,” the investigational center must enter into a Clinical Study Agreement with the sponsor that details the financing of the study as well as the rights and obligations of the investigational center and the investigator.

The WATCHMAN FLX CT study will be conducted in accordance with the International Standard ISO 14155 Clinical Investigation of Medical Devices for Human Subjects – Good Clinical Practice; relevant parts of the International Conference on Harmonisation (ICH) Guidelines for Good Clinical Practices (GCP); ethical principles that have their origins in the Declaration of Helsinki; and pertinent individual country/state/local laws and regulations. The study shall not begin until the required approval/favorable opinion from the IEC and/or regulatory authority has been obtained, if appropriate. Also, the study shall not begin prior to issuance of the center Authorization to Enroll, as provided by the sponsor. Any additional requirements imposed by the IEC or regulatory authority shall be followed, if appropriate.

Boston Scientific Corporation considers data collected from clinical trial subjects to be personal data (see definitions of different data categories in **Table 23.2-1**) and compliance with privacy and data protection laws and regulations (for example, the General Data Protection Regulation [GDPR]) to be critically important. Data collection for this clinical study has been carefully considered to comply with data privacy laws.

14.2. *Investigator Responsibilities*

The Principal Investigator of an investigational center is responsible for ensuring that the study is conducted in accordance with the Clinical Study Agreement, the clinical investigation plan/protocol, ISO 14155 or ICH/GCP, ethical principles that have their origins in the Declaration of Helsinki, any conditions of approval imposed by the reviewing IEC, and prevailing local and/or country laws and/or regulations, whichever affords the greater protection to the subject.

The Principal Investigator’s responsibilities include, but are not limited to, the following.

- Prior to beginning the study, sign the Clinical Study Agreement and comply with the Investigator responsibilities as described in such Agreement.

- Provide his/her qualifications and experience to assume responsibility for the proper conduct of the study and that of key members of the site team through up-to-date curriculum vitae or other relevant documentation and disclose potential conflicts of interest, including financial, that may interfere with the conduct of the clinical study or interpretation of results.
- Complete training requirements associated with the WATCHMAN FLX™ Left Atrial Appendage Closure Device.
- Make no changes in or deviate from this protocol, except to protect the life and physical well-being of a subject in an emergency; document and explain any deviation from the approved protocol that occurred during the course of the clinical investigation.
- Create and maintain source documents throughout the clinical study and ensure their availability with direct access during monitoring visits or audits; ensure that all clinical-investigation-related records are retained per requirements.
- Ensure the accuracy, completeness, legibility, and timeliness of the data reported to BSC in the CRFs and in all required reports.
- Record, report, and assess (seriousness and relationship to the device/procedure) every adverse event as applicable per the protocol and observed device deficiency.
- Report to BSC, per the protocol requirements, all reportable events.
- Report to the IEC and regulatory authorities any SAEs and device deficiencies that could have led to a SADE and potential/USADE, if required by applicable laws or regulations or this protocol or by the IEC, and supply BSC with any additional requested information related to the safety reporting of a particular event.
- Allow BSC and its representatives to perform monitoring and auditing activities and be accessible to the clinical research monitor or auditor and respond to questions during monitoring visits or audit(s).
- Allow and support regulatory authorities and the IEC when performing auditing activities.
- Ensure that informed consent is obtained in accordance with applicable laws, this protocol, and local IEC requirements.
- Provide adequate medical care to a subject during and after a subject's participation in a clinical study in the case of adverse events, as described in the ICF.
- Inform the subject of the nature and possible cause of any adverse events experienced.
- Inform the subject of any new significant findings occurring during the clinical investigation, including the need for additional medical care that may be required.
- Provide the subject with well-defined procedures for possible emergency situations related to the clinical study, and make the necessary arrangements for emergency

treatment, including decoding procedures for blinded/masked clinical investigations, as needed.

- Ensure that clinical medical records are clearly marked to indicate that the subject is enrolled in this clinical study.
- Ensure that, if appropriate, subjects enrolled in the clinical investigation are provided with some means of showing their participation in the clinical investigation, together with identification and compliance information for concomitant treatment measures (contact address and telephone numbers shall be provided).
- Inform, with the subject's approval or when required by national regulations, the subject's personal physician about the subject's participation in the clinical investigation.
- Make all reasonable efforts to ascertain the reason(s) for a subject's premature withdrawal from clinical investigation while fully respecting the subject's rights.
- Ensure that an adequate investigation center team and facilities exist and are maintained and documented during the clinical investigation.

All investigators will provide their qualifications and experience to assume responsibility for their delegated tasks through up-to-date curriculum vitae or other relevant documentation and disclose potential conflicts of interest, including financial, that may interfere with the conduct of the clinical study or interpretation of results.

